14.0 BIOSTATISTICS

11.1 Primary Objective

The primary objective of this study is to compare best overall response (BOR) rate by 96 weeks as determined by the investigator using RECIST 1.1 criteria between patients receiving Nivolumab and SBRT and those receiving Nivolumab alone. BOR rate is defined as the number of patients randomized to a given arm with a best overall response of complete response (CR) or partial response (PR) of non-irradiated lesions divided by the total number of patients randomized to the given arm. In order to ascertain this endpoint, efforts will be made so that patients will be followed for 96 weeks or until progression of disease (and treatment cessation), whichever comes first.

Based upon an estimated ORR of 15% in a PD-L1 unselected population in the Nivolumab alone arm (based on data from Siewert, et al; see background) and an ORR of 45% in the Nivolumab and SBRT arm, the enrollment of 54 patients with a two-sample proportion test will provide a one-sided alpha of 0.10 and a power of 0.80. Assuming a 10% drop-out rate, we will enroll a total of 60 patients. Patients will be randomized to the two treatment arms in a 1:1 ratio. Patients will be stratified based upon viral status (virus negative versus virus positive; virus status is defined by EBV (EBER testing) or HPV (p16, HPV ISH, HPV PCR) testing). Assuming a constant enrollment of 3 subjects per month, it would take approximately 20 months to randomize 60 patients. Calculations were completed using software R 3.1.1 and EAST 6.

To ensure eligible endpoints are well defined, a minimum of 6 months of follow up after treatment initiation is required. Patients lost to follow-up prior to 6 months (24 week scan) will be replaced, regardless of response. Patients lost to follow-up between 6 months and 24 months will be included in the ORR calculation.

Secondary objectives:

OS and PFS will be evaluated by the regular survival analysis tools such as Kaplan-Meier and competing risks methods. Comparisons will be conducted between the two arms by the stratified log-rank test and Gray's test.

The DOR will be calculated from the time of response to progression or last follow up and analyzed using the Kaplan-Meier method among patients who showed response.

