For the exploratory objectives, all lab measurements will be summarized and descriptive statistics will be provided. When correlation between lab measurements and treatment outcomes are of interest, Wilcoxon rank sum tests will be conducted to examine the difference between responders and non-responders within each arm. An exploratory multivariate logistic regression analysis to determine whether, once adjusted for relevant clinical covariates and treatment arm, tumor PD-L1 or serum immunophenotypic changes predict for response to Nivolumab.

To clarify we define population for the above analyses

- Randomized subjects for ORR analysis: all enrolled subjects who were randomized and provided at least 6 months of follow-up after treatment initiation. This is the dataset for the primary objective and irORR.
- All randomized subjects: all enrolled subjects who were randomized. This is the dataset for baseline demographics and time-to-event endpoints (PFS, OS).
- Treated subjects: all randomized subjects who received at least one dose of study drug. This is the dataset for safety evaluation. For instance, if a subject receives a single dose of Nivolumab but withdraws from study prior to the first dose of radiation, that subject will be considered treated.
- Biomarker Subjects: all randomized subjects with available biomarker data.
- PRO subjects: all subjects with available Patient Reported Outcomes (PRO) data.

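### The primary ORR has two written denominators: all patients randomised, and only those with at least 6 months of follow-up

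*Combined protocol and SAP*

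**What the plan says.** Section 2.1 (Primary Objective), Section 12.1 (Primary Endpoint) and Section 14.0 (under the subheading numbered 11.1) all give the same ratio: patients with a best response of CR or PR, "divided by the total number of patients randomized to the given arm".

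The list of analysis populations that closes Section 14.0 defines the ORR set differently, as "all enrolled subjects who were randomized and provided at least 6 months of follow-up after treatment initiation", and adds: "This is the dataset for the primary objective and irORR". The next entry in that list is a separate set of all randomised patients, which is assigned to baseline demographics, PFS and OS, not to ORR.

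The primary-objective text of Section 14.0 also leans towards the restricted set. It requires at least 6 months of follow-up and then says: "Patients lost to follow-up prior to 6 months (24 week scan) will be replaced, regardless of response". The sentence after that reads: "Patients lost to follow-up between 6 months and 24 months will be included in the ORR calculation". The same section says efforts will be made so that "patients will be followed for 96 weeks or until progression of disease (and treatment cessation), whichever comes first".

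**The concern.** The two definitions give different denominators and can give different numerators, so two analysts working from the same data could report different primary results. The choice could also be made after open-label results are visible.

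Under the restricted definition:

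- A randomised patient who never starts treatment cannot qualify, because follow-up is counted from treatment initiation.
- A patient lost before 6 months leaves the analysis even with a confirmed response. Scans fall at weeks 8 and 16 (Section 4.2, Intervention), and confirmation needs at least 4 weeks (Section 12.1.10), so a response can be confirmed at week 16, before the 24-week cut-off.
- It is unclear whether death or progression before 6 months counts as completed follow-up. The primary-objective text ends follow-up at progression; the population definition makes no such exception. Section 3.2 cites a median PFS of 6 months or less in recurrent disease with a metastatic component, so many patients could be affected.
- One possible route of loss exists only in Arm 2. CT simulation comes after randomisation (Section 9.1), and a plan that exceeds the dose constraints can lead to withdrawal from the study (Section 9.2.1, Target Selection). The treated-subjects definition foresees a related case, "if a subject receives a single dose of Nivolumab but withdraws from study prior to the first dose of radiation", and keeps that patient for safety, but does not say how the patient counts for ORR.

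Patients who only stop treatment are not necessarily lost: Section 4.2 continues their scans when they stop for reasons other than progression. Read alone, the replacement sentence does not say that the replaced patient leaves the denominator. The explicit exclusion comes from the population definition.

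**Working it through.** **Inputs from Section 14.0.** ORR 15% versus 45%, one-sided alpha 0.10, power 0.80, two-sample proportion test, 54 patients raised to 60 for 10% drop-out, 1:1 allocation.

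**The plan's own figure.** Without continuity correction, n per arm = [1.2816·√(2·0.30·0.70) + 0.8416·√(0.15·0.85 + 0.45·0.55)]² / 0.30² = (0.8306 + 0.5154)² / 0.09 = 20.1, so 21 per arm (42 in total). With correction, n = (20.13/4)·[1 + √(1 + 4/(20.13·0.30))]² = 26.4, so 27 per arm and 54 in total, as stated; 54/0.9 = 60. The corrected test has the same exact power as Fisher at 27 and at 30 per arm (0.807 and 0.856). The plan does not say which version will be used for analysis, so results below are given as uncorrected z / Fisher, one-sided.

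**Assumptions.** The documents give only the 10% overall drop-out. The split between arms and the response status of those lost are assumed.

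**Can the choice of denominator change the conclusion?** Planned loss is 10% of 60 = 6 patients, here all non-responders. Example: for 5/30 versus 9/30 the pooled rate is 14/60, SE = √(0.2333·0.7667·2/30) = 0.1092, z = 0.1333/0.1092 = 1.221, p = 0.111. For 5/28 versus 9/26 the pooled rate is 14/54, SE = √(0.2593·0.7407·(1/28 + 1/26)) = 0.1194, z = 0.1676/0.1194 = 1.404, p = 0.080.

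| Loss, Arm 1:Arm 2 | All randomised | 6-month set | p uncorrected | p Fisher |
|---|---|---|---|---|
| 2:4 | 5/30 v 9/30 | 5/28 v 9/26 | 0.111 → 0.080 (reverses) | 0.180 → 0.137 |
| 2:4 | 5/30 v 10/30 | 5/28 v 10/26 | 0.068 → 0.046 | 0.116 → 0.083 (reverses) |
| 4:2 | 4/30 v 8/30 | 4/26 v 8/28 | 0.098 → 0.122 (reverses) | 0.167 → 0.202 |
| 4:2 | 6/30 v 12/30 | 6/26 v 12/28 | 0.046 → 0.062 | 0.079 → 0.105 (reverses) |
| 3:3 | 5/30 v 10/30 | 5/27 v 10/27 | 0.068 → 0.064 | 0.116 → 0.112 |

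**How often would the two definitions disagree?** Responders are binomial with 30 per arm, and the two tests are compared by exact enumeration after removing 2 and 4 non-responders. The probability of disagreement is 0.034 / 0.054 if true ORR is 15% versus 45%, 0.067 / 0.082 if 15% versus 30%, and 0.024 / 0.005 if 15% in both arms. At a 3:3 split it is 0.000 in all three cases.

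**False-positive rate.** True ORR is 15% in both arms, 30 are randomised per arm, only non-responders are excluded, and there is no replacement. The response probability in the remaining n patients is 4.5/n.

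| Excluded, Arm 1 v Arm 2 | Remaining | Uncorrected / Fisher |
|---|---|---|
| none | 30 v 30 | 0.107 / 0.055 |
| 10% v 10% | 27 v 27 | 0.105 / 0.053 |
| 2 v 4 patients | 28 v 26 | 0.129 / 0.058 |
| 4 v 2 patients | 26 v 28 | 0.082 / 0.039 |
| 10% v 20% | 27 v 24 | 0.151 / 0.072 |
| 10% v 30% | 27 v 21 | 0.183 / 0.097 |

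If the arms are refilled to 30, the last row becomes 0.221 / 0.128. If instead exactly 3 and 9 non-responders are removed from binomial(30) counts, Fisher gives 0.103, so whether Fisher stays under 0.10 in that extreme row depends on the model. If loss is unrelated to response, the rates are 0.107 / 0.044 at 28 v 26 and 0.099 / 0.039 at 27 v 21.

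**The case against.** An evaluable-patient set fixed in advance can be a legitimate choice in a one-sided 0.10 screening trial, and the numerical effect is small in the likeliest cases. Several points stand:

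- Equal loss between arms, or loss unrelated to response, causes no material inflation. The replacement rule applies whatever the response, so assuming that only non-responders are lost leans towards harm.
- The uncorrected z-test is not the version that reproduces the planned 54. Under Fisher, which has the same power as the corrected test, the false-positive rate at the planned 10% loss is 0.039 to 0.058 in the scenarios tabulated, inside the nominal 0.10.
- The Arm 2 route is uncertain. Section 13.1 lists a radiation plan without approval among the reasons nivolumab ends, and Section 4.2 would then continue scans, so such patients might reach 6 months. Section 9.2.1 says they leave the study. The inclusion criteria in Section 6.2 also screen lesions against the constraints, and Section 9.2.1 allows permission to exceed them except in re-irradiation. The frequency is unknown.
- A documented death or progression is not ordinarily a loss to follow-up, so that ambiguity comes mainly from the population definition.

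These points limit the size of the effect. They do not remove the conflict: the plan states the all-randomised denominator three times, then assigns the primary objective to a different set while reserving the all-randomised set for other endpoints.

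**Conclusion.** The concern holds, and the text must be corrected before analysis. The primary endpoint has two incompatible denominators, and the restricted one makes the comparison conditional on post-randomisation events. The likely numerical effect is modest. At the planned 10% loss with a 2:4 or 4:2 split of non-responders, a result near the threshold can reverse in either direction; at the 2:4 split the two definitions disagree with probability of at most 0.082 in the scenarios examined. At an even split the figure is zero. Larger inflation needs strongly unequal loss concentrated in non-responders. All loss patterns are assumptions. The need for correction rests on the contradiction in the primary analysis and on the fact that the choice can change the conclusion, not on a large expected bias.

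**What to change.** - State in Section 14.0 that the primary ORR analysis includes all randomised patients by assigned arm, and that anyone without a confirmed CR or PR by week 96 counts as a non-responder.
- Remove the 6-month condition from the primary dataset and delete the replacement sentence; enrolment is already raised from 54 to 60 for drop-out. Align the two neighbouring sentences in Section 14.0 (the 6-month minimum, and the inclusion of losses between 6 and 24 months) so that neither still implies an exclusion.
- Keep the 6-month set as a labelled sensitivity analysis. Define loss to follow-up, and say whether death or progression before 6 months counts as completed follow-up.
- State that patients withdrawn under Section 9.2.1 stay in the Arm 2 denominator, and reconcile that section with Section 13.1 on whether their assessments continue. No treatment or removal rule needs to change for the analysis.

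The cost is a wording amendment and no extra patients. Observed ORR will be somewhat lower, and power will depend on loss. With 30 per arm and loss unrelated to response counted as non-response, the rates become 15%·(1−e) and 45%·(1−e) for loss e. Exact power (uncorrected / Fisher) is then 0.92 / 0.86 at no loss, 0.88 / 0.80 at 10%, 0.84 / 0.74 at 20% and 0.79 / 0.67 at 30%. The stated 0.80 is kept under both tests at the planned 10%, but not under Fisher at 20%.

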15.1 RESEARCH PARTICIPANT REGISTRATION AND RANDOMIZATION PROCEDURES

15.2 Research Participant Registration

Confirm eligibility as defined in the section entitled Criteria for Patient/Subject Eligibility.

Obtain informed consent, by following procedures defined in section entitled Informed Consent Procedures.

During the registration process registering individuals will be required to complete a protocol specific Eligibility Checklist.

All participants must be registered through the Protocol Participant Registration (PPR) Office at Memorial Sloan Kettering Cancer Center. PPR is available Monday through Friday from 8:30am – 5:30pm at [contact]. Registrations must be submitted via the PPR Electronic Registration System (<http://ppr/>). The completed signature page of the written consent/RA or verbal script/RA, a completed Eligibility Checklist and other relevant documents must be uploaded via the PPR Electronic Registration System.

15.3 Randomization

Patients will be randomized to the Nivolumab and SBRT arm or Nivolumab only arm. For patients enrolled, immediately after consent is obtained, the RSA at MSKCC will register participants in the Protocol Participant Registration (PPR) system. Once the participant's eligibility is established the registration will be finalized and the participants will be randomized using the Clinical Research Database (CRDB). Randomization will be accomplished by the method of random permuted block, and will be stratified by viral status (positive or negative). After treatment arm is determined by randomization, RSAs will notify the physicians at MSKCC of the treatment arm and participant ID via email within 24 hours of randomization. All Data will be collected and analyzed at MSKCC. Compiled data will be submitted to the biostatistician on study ([name]) for analysis.

16.1 DATA MANAGEMENT ISSUES

Data will be managed by a designated RSA from the Department of Radiation Oncology at MSKCC. All data will be managed in compliance with institutional policy and kept in iMedidata.

List of variables and population characteristics

- Patient demographic data (date of birth, height, weight)
- Medical history
- Concomitant medication
- Adverse events
- Laboratory Values
- Tumor Assessment Data
- Quality of Life Assessment Data
- Tumor PD-L1 status
- MDSC results

16.2 Quality Assurance

Routine data-quality reports will be generated to assess missing data and inconsistencies. Accrual rates, and extent and accuracy of evaluations and follow-up, will be monitored periodically throughout the study period and potential problems will be brought to the attention of the study team for discussion and action.

Random-sample data quality and protocol compliance audits will be conducted by the study team, at a minimum of once per year, more frequently if indicated.

16.3 Data and Safety Monitoring

The Data and Safety Monitoring (DSM) Plans at MSKCC were approved by the National Cancer Institute in September 2001. The plans address the new policies set forth by the NCI in the document entitled "Policy of the National Cancer Institute for Data and Safety Monitoring of Clinical Trials" which can be found at <http://deainfo.nci.nih.gov/grantspolicies/datasafety.htm>. The DSM Plans at MSKCC were established and are monitored by the Office of Clinical Research. The MSKCC Data and Safety Monitoring Plans can be found on the MSKCC Intranet at <http://mskweb2.mskcc.org/irb/index.htm>.

There are several different mechanisms by which clinical trials are monitored for data, safety, and quality. There are institutional processes in place for quality assurance (e.g., protocol monitoring, compliance and data verification audits, therapeutic response, and staff education on clinical research quality assurance) and departmental procedures for quality control, plus there are two institutional committees that are responsible for monitoring the activities of our clinical trials programs. The committees, *Data and Safety Monitoring Committee (DSMC)* for Phase I and II clinical trials, and the *Data and Safety Monitoring Board (DSMB)* for Phase III clinical trials, report to the Center's Research Council and Institutional Review Board.

During the protocol development and review process, each protocol will be assessed for its level of risk and degree of monitoring required. Every type of protocol (e.g., National Institutes of Health sponsored, in-house sponsored, industrial sponsored, National Cancer Institute cooperative group, etc.) will be addressed and the monitoring procedures will be established at the time of protocol activation.

17.1 PROTECTION OF HUMAN SUBJECTS

Prior to enrollment of each patient, the risks, benefits, and objectives of the study will be reviewed with the participant, including a discussion of the possible toxicities and side effects. Alternative, non-protocol, treatment options will be discussed with the patient. It will be reviewed that participation in this clinical trial is voluntary and that the patient may withdraw consent at any time. The study is designed with careful safety monitoring for toxicity including physician visits and lab work. Specific guidelines for symptom management are in place to protect the study participant.

Human Subjects Involvement and Characteristics: all patients at MSKCC who meet the inclusion criteria will be eligible. Both men and women and members of all ethnic groups are eligible for this trial.

Consent Process: all patients who meet the inclusion criteria will be eligible. Participation is voluntary. All patients will be required to sign a statement of informed consent, which must conform to IRB guidelines. The informed consent procedure is described in Section 18.0.

Possible Toxicities/Side Effects: there are risks associated with treatment as described in Section 11.0; however, patients screened for enrollment will be deemed appropriate for treatment independent on this study.

Benefits: Image-Guided, high dose radiotherapy has the potential to augment tumor response to Nivolumab.

Costs: patients will be charged for physician visits, routine laboratory tests, radiologic studies, and radiation therapy. The patients will not be billed for Nivolumab.

Alternatives: the alternative to this trial would be either standard cytotoxic chemotherapy or enrollment on other, open trials in HNSCC.

Confidentiality: every effort will be made to maintain patient confidentiality. Research and hospital records are confidential. Patients' names and any other identifying information will not be used in reports or publications resulting from this trial. Other authorized agencies and appropriate internal personnel and external personnel (monitors from BMS), its authorized agents, the FDA, and other governmental agencies may review patient records as required.

Patient Safety: patients are monitored by physicians and oncology nurses who are very familiar with clinical trials. In the case of an adverse reaction, immediate medical attention is available. In the evenings and weekends, we have 24-hour urgent care facility for outpatients. The PI and co-PIs will be available at all times to organize any necessary intervention.

Monitoring of Data to Ensure Safety: this study will be monitored by the institutional IRB. This incorporates an independent data and safety monitoring committee established by arrangement with the National Cancer Institute. The analysis of safety will include all

patients' adverse events, including all toxic effects of treatment, will be tabulated individually, and summarized by severity and causality.

17.2 Privacy

MSK's Privacy Office may allow the use and disclosure of protected health information pursuant to a completed and signed Research Authorization form. The use and disclosure of protected health information will be limited to the individuals described in the Research Authorization form. A Research Authorization form must be completed by the Principal Investigator and approved by the IRB and Privacy Board (IRB/PB).

17.3 Serious Adverse Event (SAE) Reporting

An adverse event is considered serious if it results in ANY of the following outcomes:

- Death
- A life-threatening adverse event
- An adverse event that results in inpatient hospitalization or prolongation of existing hospitalization
- A persistent or significant incapacity or substantial disruption of the ability to conduct normal life functions
- A congenital anomaly/birth defect
- Important Medical Events (IME) that may not result in death, be life threatening, or require hospitalization may be considered serious when, based upon medical judgment, they may jeopardize the patient or subject and may require medical or surgical intervention to prevent one of the outcomes listed in this definition

Note: Hospital admission for a planned procedure/disease treatment is not considered an SAE.

Suspected transmission of an infectious agent via the study drug is an SAE.

Although pregnancy, overdose, cancer, and potential drug induced liver injury are not always serious by regulatory definition, these events must always be handled as an SAE.

Any component of a study endpoint that is considered related to the study therapy (radiation or Nivolumab) should be reported as an SAE.

SAE reporting is required as soon as the participant signs consent and is registered. SAE reporting is required for 30-days after the participant's last investigational treatment or intervention. Any events that occur after the 30-day period and that are at least possibly related to protocol treatment must be reported.

An SAE must be reported to the IRB/PB within 5 calendar days of the event. The IRB/PB requires a Clinical Research Database (CRDB) SAE report should be submitted electronically to the SAE Office as follows:

For IND/IDE trials: Reports that include a Grade 5 SAE should be sent to [contact]. All other reports should be sent to [contact].

The report should contain the following information:

Fields populated from Medidata:

- Subject's name (generate the report with only initials if it will be sent outside of MSK)
- Medical record number
- Disease/histology (if applicable)
- Protocol number and title

Data needing to be entered:

- The date the adverse event occurred
- The adverse event
- The grade of the event
- Relationship of the adverse event to the treatment (drug, device, or intervention)
- If the AE was expected
- The severity of the AE
- The intervention
- Detailed text that includes the following
 - A explanation of how the AE was handled
 - A description of the subject's condition
 - Indication if the subject remains on the study
 - If an amendment will need to be made to the protocol and/or consent form.

The PI's signature and the date it was signed are required on the completed report.

For IND/IDE protocols:

The CRDB AE report should be completed as above. If appropriate, the report will be forwarded to the FDA by the SAE staff through the IND Office.

17.2.1

SAEs, whether related or not related to study drug, and pregnancies must be reported to BMS within 24 hours. SAEs must be recorded on BMS or an approved form; pregnancies on a Pregnancy Surveillance Form.

SAE Email Address: [contact]

SAE [contact]

If only limited information is initially available, follow-up reports are required. (Note: Follow-up SAE reports should include the same investigator term(s) initially reported.)

If an ongoing SAE changes in its intensity or relationship to study drug or if new information becomes available, a follow-up SAE report should be sent within 24 hours to the BMS (or designee) using the same procedure used for transmitting the initial SAE report.

All SAEs should be followed to resolution or stabilization.

For studies conducted under an Investigator IND in the US include the following:

For studies conducted under an Investigator IND in the US, any event that is both serious and unexpected must be reported to the Food and Drug Administration (FDA) as soon as possible and no later than 7 days (for a death or life-threatening event) or 15 days (for all other SAEs) after the investigator's or institution's initial receipt of the information. BMS will be provided with a simultaneous copy of all adverse events filed with the FDA.

SAEs should be reported on MedWatch Form 3500A, which can be accessed at: <http://www.accessdata.fda.gov/scripts/medwatch/>.

MedWatch SAE forms should be sent to the FDA at:

MEDWATCH

[name]

[name]

Fax: [name] ([name])

<http://www.accessdata.fda.gov/scripts/medwatch/>

All SAEs should simultaneously be faxed or e-mailed to BMS at:

Global Pharmacovigilance & Epidemiology

Bristol-Myers Squibb Company

[contact]

Email: [contact]

- An SAE report should be completed for any event where doubt exists regarding its seriousness.
- For studies with long-term follow-up periods in which safety data are being reported, include the timing of SAE collection in the protocol.
- If the investigator believes that an SAE is not related to study drug, but is potentially related to the conditions of the study (such as withdrawal of previous therapy or a complication of a study procedure), the relationship should be specified in the narrative section of the SAE Report Form.
- If only limited information is initially available, follow-up reports are required. (Note: Follow-up SAE reports should include the same investigator term(s) initially reported.)
- If an ongoing SAE changes in its intensity or relationship to study drug or if new information becomes available, a follow-up SAE report should be sent within 48 hours to BMS using the same procedure used for transmitting the initial SAE report. All SAEs should be followed to resolution or stabilization. All SAEs should be followed to resolution or stabilization.

